#### Exclusion Criteria

- Patients  $< 18$  years of age
- Patients who are unable to provide informed consent
- Patients without a positive COVID-19 PCR result obtained through nasopharyngeal swab
- Patients with a COVID-19 diagnosis but without self-reported anosmia
- Patients with severe COVID-19 disease as defined by the Mount Sinai Health System Treatment Guidelines for SARS-COV-2 (requiring high flow nasal cannula, non-rebreather, CPAP/BIPAP, or mechanical ventilation OR patients requiring pressor medication OR patients with evidence of end organ damage)
- Patients with pre-existing self-reported olfactory dysfunction
- Patients with a history of chronic nasal/sinus infections (rhinosinusitis) or history of endoscopic sinus surgery
- Patients using nasal steroid sprays or irrigations for any reason
- Patients who are prisoners of the state
- Patients who have psychiatric or developmental disorder conditions that may impair ability to provide informed consent

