## Summary

### Objectives:

#### Research Questions:

1. What is the natural history of COVID-19 related olfactory dysfunction?
2. Is there a therapeutic benefit of omega-3 supplement administration for COVID-19 related olfactory dysfunction?

The aim of the study is to gain an understanding of the natural history of olfactory dysfunction associated with COVID-19 infection in addition to evaluating whether there is a therapeutic role for omega-3 supplementation during the subacute period. Through this study, we hope to provide anticipatory guidance regarding the prognosis for COVID-19 related olfactory dysfunction as well as assess a potential therapeutic intervention.

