## **Risk and Benefits**

## Risks to Subjects

Patients will be randomized into treatment and control groups. The treatment group will receive omega-3-fatty acid supplementation (1000 mg of omega-3 fatty acid blend including 683 mg Eicosapentaenoic Acid and 252 mg Docosahexaenoic Acid) to be taken daily for 6 weeks. The control arm will receive a placebo pill to be taken twice daily.

The main risks to subjects that choose to participate are as following:

-BSIT: This 12-item version of the Smell Identification Test™ is useful for quantifying smell loss in situations where less than five minutes of time are available. The odors are well known in most cultures. There are no side effects known to occur from this test. Patients could theoretically experience some nausea, vomiting, or headache from the different smells.

-Omega-3 fish oil has been deemed "generally regarded as safe" by the Federal Drug Administration and is considered to be very rarely associated with significant adverse side effects. Side effects of omega-3 fatty acid supplementation are typically mild and include gastrointestinal discomfort, heartburn, headache, and unpleasant taste. Patients also sometimes note a fishy odor or taste in their mouth that they find unpleasant. Taking high doses of fish oil supplements can potentially increase the risk of bleeding. However this is associated with much higher dosing and duration than what will be utilized during this study. A 2018 Chang et al. meta-analysis of 21 randomized clinical trials involving a total of 12,750 patients receiving omega-3 fatty acid supplementation found no serious adverse events, concluding that they are generally safe and well-tolerated but are associated with these mild side effects. No patient-reported adverse events were reported in the 2020 Yan et al. randomized control study on omega-3 fatty acid supplementation after skull base surgery.

2 Chang, C. H. et al. Safety and tolerability of prescription omega-3 fatty acids: A systematic review and meta-analysis of randomized controlled trials. *Prostaglandins Leukot Essent Fatty Acids* 129, 1-12, doi:10.1016/j.plefa.2018.01.001 (2018).

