### Description of Procedures Being Performed

Patients will be recruited (utilizing inclusion and exclusion criteria outlined above) through the Otolaryngology Faculty Practices as well as the web based application STOP COVID NYC. Current recruitment goals are one hundred seventy six patients, with eighty eight patients in each group. After recruitment the patients will be block-randomized by a computer-generated sequence in a 1:1 allocation to treatment or control arms. Patients randomized to the treatment group will be allocated a supply of 1000 mg capsules of omega-3 fatty acid blend including 683 mg Eicosapentaenoic Acid and 252 mg Docosahexaenoic Acid) to be taken daily for 6 weeks. Patients randomized to the control group will receive a placebo and will follow the same regimen as the treatment group. Collection of data (described below) will occur through the use of the EPIC electronic medical record system, through phone conversations between investigators and subjects, and through information collected during office visits. The primary outcome studied will be the Brief Smell Identification Test (BSIT) which will be administered 6 weeks after symptom onset. The secondary outcomes include patient-reported outcome measure surveys, a modified Brief Questionnaire of Olfactory Dysfunction - Negative Statements (QOD-NS) survey and Sino-Nasal Outcome Test (SNOT-22), administered at time points of 1, 2, 4, and 6 weeks after symptom onset. After the conclusion of data collection a statistical analysis will be conducted to compare outcomes in the treatment and placebo arms.

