## **Data**

### Description of Health Information that Will Be Viewed, Recorded, Or Generated

1. Data at the initial visit will include:
2. Documentation that patient meets all inclusion criteria and no exclusion criteria
3. Patient Identifying information (DOB, Name, MRN) and a Subject ID will be assigned
4. Patient's home address will be obtained in order to send BSIT kit and placebo or supplement.
5. Demographic information including age, gender, race and ethnicity
6. Patient history - history of present illness (including presence of symptoms, onset and duration of symptoms, associated symptoms, past medical history, past surgical history)
7. Past medical history
8. Past surgical history
9. List of medications and medication allergies
10. Brief Questionnaire of Olfactory Dysfunction - Negative Statements (QOD-NS) Score
11. Sino-Nasal Outcome Test (SNOT-22) Score
12. Follow-up visits at 1 week, 2 weeks and 4 weeks:
13. Patient interval history
14. Brief Questionnaire of Olfactory Dysfunction - Negative Statements (QOD-NS) Score
15. Sino-Nasal Outcome Test (SNOT-22) Score
16. Follow-up visit at 6 weeks:
17. Patient interval history
18. Brief Smell Identification Test (BSIT) Score
19. Brief Questionnaire of Olfactory Dysfunction - Negative Statements (QOD-NS) Score

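### Patients already taking omega-3 or fish oil are not excluded, and off-study use is not specifically recorded, so the tested product can be present in the placebo arm and dilute the comparison

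*Protocol*

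**What the plan says.** The second research question in the Summary is "Is there a therapeutic benefit of omega-3 supplement administration for COVID-19 related olfactory dysfunction". Under Risks to Subjects, "The treatment group will receive omega-3-fatty acid supplementation" daily for six weeks, and the other arm receives placebo.

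Inclusion Criteria admit adults with self-reported new-onset olfactory dysfunction and a positive COVID-19 diagnosis. Exclusion Criteria list ten items. Only one concerns use of a product: "Patients using nasal steroid sprays or irrigations for any reason". Omega-3 and fish oil do not appear.

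The nearest rule on conduct during treatment is in Procedures for Investigator to Withdraw Subjects. It concerns adherence to the blinded study product, not supplements obtained elsewhere. The procedures, risk and safety-monitoring sections contain no rule on other supplements.

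At the initial visit the study collects, among other items, "List of medications and medication allergies" (Description of Health Information). No eligibility rule is attached to that list, and supplements are not mentioned. The follow-up contacts at 1, 2, 4 and 6 weeks collect an interval history, again with no mention of supplements.

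**The concern.** The protocol treats a concurrent olfactory treatment as a reason for exclusion. The Background describes nasal steroid irrigations, combined with smell retraining, as possibly beneficial, and the exclusion list removes nasal steroid users. The same reasoning applies at least as strongly to the product under test. The protocol itself calls that product a supplement, so use before enrolment is foreseeable.

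A user randomised to placebo is not an omega-3-free control. A user randomised to active treatment takes the study capsule on top of existing intake. In both cases the difference in exposure between arms may not be the one the research question assumes. What is at stake is the size of the detectable difference, and how confidently a null result could be read as absence of benefit.

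**Working it through.** **Inputs from the protocol.** "Current recruitment goals are one hundred seventy six patients, with eighty eight patients in each group", "block-randomized by a computer-generated sequence in a 1:1 allocation to treatment or control arms". The primary outcome is the BSIT at 6 weeks after symptom onset.

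**Inputs not in the protocol.** Alpha, power, target effect, standard deviation, dropout and the share of patients taking omega-3 are not stated. The figure of 88 per arm therefore cannot be reproduced from the document. The following are assumed for illustration: two-sided alpha 0.05, a comparison of two means (normal approximation), no dropout, and a user share c of 5%, 10% or 20%.

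**Step 1: the effect that 88 per arm can detect.** δ = (z₀.₉₇₅ + z_power) × √(2/88), in standard deviation units.
- 80% power: (1.960 + 0.842) × 0.1508 = 0.422. A t-test calculation gives 0.425, with the same power figures below.
- 90% power: (1.960 + 1.282) × 0.1508 = 0.489.

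**Step 2: dilution.** Let k be the fraction of the between-arm contrast that users keep. With the same user share in both arms, as randomisation gives on average, the observed effect is δ × m, where m = 1 − c(1 − k).
- k = 0 is the worst case. Off-study omega-3 already gives the full effect and the study capsule adds nothing, so m = 1 − c.
- k = 0.5 lets the capsule add half its effect in users, so m = 1 − c/2.

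Any small change in the standard deviation from mixing users and non-users is ignored.

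**Step 3: power at 88 per arm.** For the 80% case, power = Φ(2.802 × m − 1.960). The number per arm that restores 80% is 88/m², rounded up.

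| User share | m, k = 0 | Power | Per arm for 80% | m, k = 0.5 | Power | Per arm for 80% |
|---|---|---|---|---|---|---|
| 0% | 1.000 | 80.0% | 88 | 1.000 | 80.0% | 88 |
| 5% | 0.950 | 75.9% | 98 | 0.975 | 78.0% | 93 |
| 10% | 0.900 | 71.3% | 109 | 0.950 | 75.9% | 98 |
| 20% | 0.800 | 61.1% | 138 | 0.900 | 71.3% | 109 |

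For the 10% row with k = 0: 2.802 × 0.9 − 1.960 = 0.561, and Φ(0.561) = 0.713.

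**Step 4: sensitivity to the assumed effect.** If 88 per arm instead had 90% power, power = Φ(3.242 × m − 1.960). With k = 0 this gives 86.9%, 83.1% and 73.7% at 5%, 10% and 20% users.

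**The case against.** **The comparison is unbiased, and this may be a deliberate choice.** Users are balanced by randomisation, and the effect of adding a capsule to usual intake is a legitimate pragmatic question. That much stands. A reader might infer that the gap biases the trial, and the documents do not support this. But the protocol nowhere says that it intends the add-on question, and it removes nasal steroid users rather than randomising over them.

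**The power losses could be read as forecasts.** They are not. The user share and the effect are assumed. The k = 0 column also requires the study capsule to do nothing for users, although a user in the active arm takes it on top of existing intake. For each share, that column is a floor within the range shown. The k = 0.5 column gives a milder case.

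**Use may be recorded already.** A reader might infer that a null result could not be told apart from contamination. That is too strong. A baseline medication list and interval histories are collected. If supplements are entered there, users can be described or set aside in a sensitivity analysis, which an analysis plan not shown here may specify. This is only partial mitigation, because the protocol does not ask about supplements and recording use does not restore lost contrast.

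**Placebo patients might buy omega-3 once they know what is being tested.** This is plausible, but no consent text shown says what patients are told. The same limit applies in the other direction: some sections were removed and the Drugs/Biologics section has no visible text, so an instruction on supplements could exist elsewhere. The point rests on use at entry and does not need this inference.

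**Conclusion.** The point holds as a gap in eligibility and data capture. The visible text excludes users of one other olfactory treatment but not users of the tested product, and it neither restricts nor specifically records off-study use. Eligibility belongs in the protocol, and an analysis plan cannot recover contrast lost at enrolment.

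The consequence is dilution and a null result that is harder to interpret, without bias between arms. For an effect detectable with 80% power, the loss is about 4 to 19 percentage points in the worst case across 5% to 20% users, and about 2 to 9 points if users keep half the contrast. These figures rest on the assumed shares, alpha and effect. The direction is the same in every case with k below 1. If very few patients take omega-3, or if the capsule works fully on top of existing intake, the loss is negligible. The protocol should be changed, but the gap does not invalidate the trial.

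**What to change.** Add an exclusion criterion for patients currently taking an omega-3 or fish-oil supplement, and check it against the medication list already taken at the initial visit, with supplements named explicitly. Record any off-study omega-3 use in the interval history at weeks 1, 2, 4 and 6, and report it by arm.

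The work is one eligibility line and one question at contacts that already exist. The real cost is a smaller eligible pool and slightly narrower generalisability. To fill 176 places, about 176/0.9 = 196 otherwise eligible patients would be needed at 10% users, and 176/0.8 = 220 at 20%. Keeping users and restoring 80% power would instead mean randomising 218 or 276 in the worst case, or 196 or 218 if users keep half the contrast. The protocol expects recruitment to be fairly easy (Feasibility of Meeting Recruitment Goals), so the smaller pool should be acceptable.

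If the sponsor prefers to keep users, the protocol should say that the question is the effect of adding the study product to usual intake. The recording and reporting by arm are still needed in that case.

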#### Other Aspects that Could Increase Subjects' Vulnerability

Patients who are minors, prisoners, or those who have a psychiatric or developmental disorder that may impair their ability to provide informed consent will be excluded from the study.

Personal health information will be protected in order to ensure that subjects' vulnerability is not increased. All research data will be accessible only to the research team members, and all data will be de-identified, encrypted, and password protected. This data will be stored on a Mount Sinai hospital computer located in the Otolaryngology Resident Library on the 10th floor of the Annenberg building. The library is locked at all times and requires a password for entry.

#### Safeguard to protect Subjects' rights and welfare

The principal and co-investigators will maintain communication with the subjects in order to help identify any issues that arise. The PI, co-investigator, or a delegate will inquire about adverse events throughout the study via phone calls and in-office visits. The PI will maintain records of all adverse events and will use the NCI Common Terminology Criteria for Adverse Events (CTCAE) for documentation. Adverse events occurring during the study will be reported to the Mount Sinai Program for the Protection of Human Subjects (PPHS). Any suspension of the study will be reported to the PI and the IRB. Additionally, a data and safety monitoring committee (DSMC) will be established and consist of the principal investigator and co-investigators. Adverse events will be reviewed every three months.

## **Participation**

### Procedures for Subjects to Request Withdrawal

Patients can request to be withdrawn from the study at any time during the recruitment or data collection period. Patients will be withdrawn from the study as requested. If a patient withdraws, all the information collected and stored will be immediately deleted.

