### Provisions to Protect the Privacy Interests of Subjects

Data will be saved on a master list of subjects kept on a secure department-owned computer. Subjects will be deidentified and assigned a code, with which all other communication and data will be saved. Subjects will be able to decide whether or not to discuss their participation in the study with individuals outside of the research study. The patient will be able to decide what private information to disclose to research personnel provided the information is not necessary for the study. Additionally, subjects will be able to decide which research personnel they would like to communicate with. Study personnel will respect subjects' decisions. All saved data will be permanently destroyed at the end of this study.

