### **Safety Monitoring:**

Patients will be asked to report adverse effects related to omega-3 use. Minor side effects are not uncommon, and typically include gastrointestinal distress or fishy test. Serious adverse events are exceedingly rare. Patients will be instructed to report any potential adverse events to the PI which will be recorded. Patients will be screened for adverse events at each of the data collection check-points (1 week, 2 weeks, 4 weeks, and 6 weeks).

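### Deleting everything held on a patient who asks to withdraw erases baseline, survey and safety data after randomisation and conflicts with the duty to keep all adverse event records

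*Protocol*

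**What the plan says.** Protocol, Procedures for Subjects to Request Withdrawal, sets the window: "Patients can request to be withdrawn from the study at any time during the recruitment or data collection period". It then sets the consequence: "If a patient withdraws, all the information collected and stored will be immediately deleted". Nothing there exempts randomised patients or adverse events.

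Protocol, Safeguard to protect Subjects' rights and welfare, sets the opposite duty for safety data: "The PI will maintain records of all adverse events and will use the NCI Common Terminology Criteria for Adverse Events (CTCAE) for documentation". The same section sends adverse events to the institution's human-subjects programme (PPHS) and sets the internal review interval: "Adverse events will be reviewed every three months".

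Protocol, Safety Monitoring, adds that "Patients will be instructed to report any potential adverse events to the PI which will be recorded" and that "Patients will be screened for adverse events at each of the data collection check-points (1 week, 2 weeks, 4 weeks, and 6 weeks").

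The Data section schedules QOD-NS and SNOT-22 at the initial visit and at 1, 2, 4 and 6 weeks, and the BSIT at 6 weeks only. Procedures for Investigator to Withdraw Subjects lists further grounds for withdrawal (not following the blinded regimen, clinical deterioration, early end of the study) but does not say what happens to the data.

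**The concern.** Ending new data collection when a patient leaves is normal. Erasing what was properly observed before that point is a different act, and it cannot be undone. Whatever a statistical analysis plan says about missing data, it cannot bring back scores or events that no longer exist, so this is a flaw in a stated protocol rule and not a detail left for later.

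Three things are at stake:

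- **Secondary endpoints.** Survey scores given before withdrawal could not enter any analysis. Baseline data would go too, so patients who withdrew could not be compared with those who stayed.
- **Natural history.** The first research question concerns the course of olfactory dysfunction, and the early course of these patients would be missing from it.
- **Safety.** An adverse event recorded before withdrawal would leave the study file although the protocol requires a record of every event. If patients with events withdraw more often than others, the reported rate is too low. If that pattern differs by arm, the comparison is distorted as well.

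**Working it through.** The plan states no figure on this point, so there is none to reproduce. The check is a comparison of rules, followed by an illustration of size.

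**1. Do the two rules conflict?** Take a randomised patient with an adverse event recorded at week 2 who asks to withdraw after the week 4 contact.

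- Under the withdrawal section, everything held is deleted at once, including the event.
- Under the safeguard section, the principal investigator keeps a record of every adverse event.
- No section gives either rule priority, so both cannot be followed for this patient.

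**2. What does this patient lose?** By the Data section's schedule: QOD-NS and SNOT-22 at the initial visit and at weeks 1, 2 and 4, so up to 4 occasions × 2 instruments = 8 scores. Also lost are demographics and history, and the findings of three adverse event screens. No BSIT is lost, because none has been taken.

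**3. Could review happen before deletion?** Follow-up lasts 6 weeks and review takes place every three months, about 13 weeks. A patient's whole participation can fall between two reviews, so an event can be recorded and deleted before the monitoring group sees it.

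**4. How many patients?** The planned number is 176, with 88 per arm (Description of Procedures Being Performed). The protocol gives no withdrawal rate, so 5% to 15% is an assumption.

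- 5%: 0.05 × 176 = 8.8, about 9 patients
- 10%: 0.10 × 176 = 17.6, about 18 patients
- 15%: 0.15 × 176 = 26.4, about 26 patients

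**5. What could this do to an adverse event rate?** Let w be the share of an arm that withdraws, a the share of those patients with a recorded event, and s the share of stayers with an event. The true rate is s(1 − w) + a·w. The rate among patients whose data are kept is s. The number of patients with events who are erased is 88·w·a. With s = 10% (assumed), the kept rate is 10% throughout:

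- w = 5%, a = 50%: true rate 0.095 + 0.025 = 12.0%; erased 88 × 0.05 × 0.50 = 2.2
- w = 10%, a = 50%: true rate 0.090 + 0.050 = 14.0%; erased 88 × 0.10 × 0.50 = 4.4
- w = 15%, a = 50%: true rate 0.085 + 0.075 = 16.0%; erased 88 × 0.15 × 0.50 = 6.6
- w = 10%, a = 10%: true rate 0.090 + 0.010 = 10.0%, so no bias in the rate; erased 88 × 0.10 × 0.10 = 0.9
- w = 10%, a = 100%: true rate 0.090 + 0.100 = 19.0%; erased 88 × 0.10 × 1.00 = 8.8

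The bias therefore depends on whether withdrawal is related to events. The documents do not settle that. The loss of records occurs either way.

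**The case against.** The strongest reply is that the rule is narrow and its effect may be small. Much of this stands.

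- **Only requested withdrawal is clearly covered.** A reader might infer that the 1-, 2- and 4-week scores would exist for completers only. The text does not say so. A patient who misses contacts or is lost to follow-up without withdrawing keeps all earlier data. Whether deletion extends to withdrawal by the investigator is not stated.
- **Stopping treatment is not leaving the study.** The section on research-related harm ends treatment after a significant adverse reaction; it does not order withdrawal or deletion. It cannot be inferred that every patient who stops because of a side effect disappears from the safety data.
- **Some events may survive elsewhere.** Reports to PPHS and entries in EPIC, the hospital record, lie outside the study file. This limits the practical loss, but it does not meet the principal investigator's own duty to maintain the records.
- **The primary endpoint is largely untouched.** Only a withdrawal requested after the 6-week test could remove a BSIT.
- **Reasons for leaving are not documented.** The protocol lists mild side effects of omega-3, such as gastrointestinal discomfort and a fishy taste, but nowhere says that patients leave because of them, because of early recovery or because of lack of improvement.

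A reader might also join this rule to the privacy section, where "All saved data will be permanently destroyed at the end of this study", and conclude that no result could ever be checked. That is a separate privacy provision. The end of the study is not defined and could come after analysis and reporting, so the stronger conclusion is not supported.

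None of this removes the conflict, or the loss for patients who do ask to withdraw.

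**Conclusion.** The point holds in a limited form. For a randomised patient who asks to withdraw, the protocol orders the immediate loss of baseline data, survey scores and adverse event records, and it contradicts its own rule that all adverse events stay on record. The damage is to the secondary surveys, the natural-history description and the safety record, and hardly at all to the primary BSIT comparison.

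The size cannot be derived from the protocol. About 9 to 26 of 176 patients rests on an assumed 5% to 15% requesting withdrawal. The safety illustration (14% true against 10% recorded) further assumes 10% withdrawal, an event in half of those who withdraw and in 10% of those who stay, and no recovery of events from outside sources.

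A reader might go further and picture a clear excess of side effects in one arm reported as none in either. That would need every affected patient to withdraw formally, no remaining patient to have an event, and no use of outside records. The protocol itself calls minor side effects not uncommon, so stayers would be expected to report some. The case for change rests on the contradiction and on a loss that cannot be reversed, not on that extreme.

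**What to change.** Replace the deletion sentence with: *If a patient withdraws, no further data are collected; data collected up to withdrawal, including survey scores and adverse events, are retained in coded form and analysed in the randomised arm.* State that the same rule covers withdrawals under Procedures for Investigator to Withdraw Subjects. This also reconciles the withdrawal section with the duty to keep adverse event records.

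Put the rule in the consent form so that patients know it before they join. The consent text was not available for this review. If patients already enrolled were promised deletion, apply the new rule to them only as far as their signed consent allows.

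The cost is a short protocol amendment and a matching sentence in the consent form, plus a check of existing consents if enrolment has begun. The downside is that a withdrawing patient can no longer have coded data erased. The sample size, visit schedule and endpoints do not change.
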